IND 37368

Date: April 18th, 2017

To: [name]., MPH, IRB Chair, NICHD IRB

Recommended by:

[name]. M.D., Ph.D., Chief, Bone & Extracellular Matrix Branch, NICHD

[name]., Ph.D., Clinical Director, NICHD

Project Title:	Studie Treatn III and	es of Growth Deficiency and Growth Hormone nent in Children with Osteogenesis Imperfecta Types 1 IV				
Principal Investigator:	[name] (Chief,	[name], M.D., Ph.D. Bone and Extracellular Matrix Branch, NICHD, NIH				
Associate Investigators:	[name] Clinica Intramu	[name], MD, Orthopaedic Surgeon-BC al and Investigative Orthopaedics Section of the ural Research Program, NIAMS				
	[name] I Nurse I NIH	[name], CRNP, MS, BSN Practitioner, Office of the Clinical Director, NICHD,				
Outside Collaborators:	[name] [name]., Department of Orthopedics, Jniversity				
	[name]	[name], Ph.D., Mayo Clinic, Rochester MN				
Estimated Duration of Study:		20 years				
Total Patients to be Recruite	ed:	60				
Normal Volunteers:		None				

Description of Patient Population: Children with Osteogenesis Imperfecta (Types III and IV), and short stature, ages **3** through 15 years.

PRECIS:

Growth deficiency is a cardinal feature of severe Osteogenesis Imperfecta (OI) and a frequent feature of mild to moderate forms of this disease. Despite the prevalence of short stature among people with OI, few studies have examined treatment options for this feature of OI. Recombinant human growth hormone (rGH) is a treatment for growth deficiency which we have investigated. In our initial studies we have found that many OI children are responsive to rGH, especially those with type IV OI. The purpose of this protocol is to examine the effect of growth hormone treatment on linear growth of children with types III and IV OI and correlate growth responsiveness with growth hormone-somatomedin axis and histomorphometry parameters of OI bone.

INTRODUCTION:

Osteogenesis Imperfecta (OI) is a heritable disorder of connective tissue with bone fragility as the hallmark feature. Classical autosomal dominant OI is caused by structural defects in the genes coding for type I collagen (*COL1A1* and *COL1A2*). [1] Growth deficiency is the most striking secondary feature of OI. Severe growth deficiency is always present in type III OI and is a frequent feature of moderate (type IV) OI. In general, the degree of growth deficiency parallels the severity of the bone disease in morphologic and radiographic features but not in fracture number. [2]

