We began investigating the status of hormones related to growth in 28 children with osteogenesis imperfecta. [11] This original investigation was prompted by the observation that several children with OI, who served as non-endocrine controls in GHD studies, did not have normal test results. Our goals were to determine 1. whether there were any abnormalities of the growth hormone / somatomedin-C axis in this condition, 2. whether any abnormalities correlated with the type of OI, and 3. whether OI bone could be safely stimulated to grow. The endocrine evaluation of the OI children included a GRF stimulation test, three standard GH provocative tests (Arginine-Insulin tolerance test, L-Dopa stimulation test), a 24 hour q 20 minute sampling for measuring basal, unstimulated concentrations of GH and a somatomedin generation test.

Endocrine evaluation of 28 patients at the NIH has shown that about half of them have a low area under the integrated curve of unstimulated 24 hour growth hormone secretion, and fail to respond positively to a growth hormone releasing hormone stimulation test or a somatomedin generation test. [12]

Complete evaluation of the hormonal axis related to growth in short children with OI revealed subtle deviations from normal in some of the children; there was no pattern of response to any test or among any sequence of tests that correlated with the type of OI or the degree of growth deficiency. The only significant correlation of test results was that 12 children, whose response to GRH was comparable to the GRH response of GHD children [13], had a significantly lower area under the 24 hour curve of unstimulated growth hormone secretion, while 14 children with a normal response to GRH also had a normal area under the 24 hour growth hormone axis even though, by standard criteria of GH provocative tests and the 24 hour GH sampling, they did not fill the criteria of growth hormone deficiency.

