The pre-treatment interval will be a one year time period during which children will be serving as their own baseline controls. The visit schedule will be every 3 months. Linear growth on each side of the body will be measured at each visit with 5 lengths using a supine length board. Other measurements at each visit will include weight, arm span, sitting height, upper and lower extremity segments, and head circumference. At 6 month intervals, radiographic assessments of spine, and lower extremities will be performed, as well as bone density of the lumbar spine. Radiographic assessments of bone age will be done annually.

Children enrolled in this protocol will be co-enrolled in protocol 97-CH-0064 and will undergo pulmonary testing and neurological imaging on the schedule for that protocol. For pulmonary function testing, the tests will be completed at Children's National Medical Center. Children too young to cooperate with the procedures of pulmonary function testing will not be sedated for these procedures. Additionally, neuroimaging studies of the head and neck, including CT and MRI scan, will commence when the child is able to cooperate without needing sedation. In our experience, children age 4-5 years are able to hold still for the CT scan, which takes approximately 5-10 minutes. If signs of Basilar Invagination (BI) are detected, the children progress to having MRI scans every year.

An iliac crest bone biopsy will be obtained at the beginning of the treatment year for growth hormone. This biopsy will be repeated at the end of the growth hormone treatment year. The biopsies will be obtained by [name] for analysis in [name] laboratory. The procedure will be performed under general anesthesia in the operating room at the NIH.

During the pre-treatment year, the following testing will be done for endocrine evaluation.

1.5cc

2.	Somatomedin Generation Test [14]	3.2 cc / draw (includes discard)
		2.0 cc added to Baseline and Day 5
		20.0 cc total

Our experience with this test in OI children shows that 89% demonstrate a peak response beginning at 48 hours after the initial injection. Therefore we plan to do the full 6 day test, but only draw blood at baseline (day 0) and days 2-5. To evaluate for the possibility of growth hormone resistance, we will measure GHBP and IGFBP-3 at baseline and day 5 of this test.

3.	IGF-I	3.0 cc
	IGFBP-3, GHBP	
	Bone Specific Alk Phos	6.0 cc
	Osteocalcin, Type I Collagen Peptide	4.0 cc
	TSH, FT ₄ , T ₄	4.0 cc

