growth hormone administration are listed in attachment I. These are expected risks and therefore will not be considered reportable to the FDA.

Adverse events that will be reported to the NICHD IRB will include those events reportable to the FDA and Eli Lilly. In addition, we will report the following adverse events related to the bone biopsy procedure:

- 1. Prolonged bleeding at the biopsy site, which we define as bleeding lasting longer than 24 hours post biopsy
- 2. Post biopsy infection at the biopsy site; defined as an infection diagnosed and treated by the private physician at home within 7 days of the biopsy.

Frequent fractures are a cardinal feature of patients with OI. Fractures may not be consistently documented by x-ray or history, and can occur in clusters. For these reasons, fracture incidence is not an accurate measure of progression or worsening of osteogenesis imperfecta. Fractures are not defined as reportable adverse events.

RADIATION EXPOSURE

The effective dose calculation for the radiographic studies involved in this protocol is 0.43 rem. The amount of radiation in this study is within the dose guideline (0.5 rem) established by the NIH Radiation Safety Committee for pediatric research subjects, and is deemed a slight increment above minimal risk. The amount of radiation that patients will receive in this protocol is equivalent to the amount of radiation exposure from natural background sources in about a year and a half. The highest individual organ exposures will be to the skin, muscle, and bone surfaces (4 rem each). The radiographic studies described in this study are acceptable to obtain the desired research information, and present the prospect of direct benefit to the individual subjects. The radiographic procedures will be performed by or under the supervision of a radiologist in the NIH CC Radiology Department.

We invite the parents of our patients to bring recent films taken at home which can be copied at the Clinical Center and returned to them, thus eliminating the need for repeat films. All parents will be informed that this is a possibility, and told to request that a ruler be placed on the long bone films.

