"For subjects who were minors at the time of consent and are now age 18 years or older, the PI has requested a waiver of consent (45 CFR.46.117) for continued analysis of their data. The research involves no more than minimal risk and a waiver will not adversely affect the rights and welfare of the subjects. The only record linking the subject and the research would be the consent document and the principal risk would be potential harm resulting from breach of confidentiality. Continued research could not be carried out without the waiver as several protocol participants signed their assent more than 10 years ago and the PI has lost touch with about 3/4 of the patients. Wherever appropriate, subjects will be provided with additional pertinent information regarding any findings learned from the analysis of their data".

Adverse Event Procedures and Documentation

All Unanticipated Problems (UP), Unanticipated Adverse Device Effects (UADE), Protocol Deviations (PD), deaths, and Adverse Events (AE) will be reported to the IRB or the Clinical Director (CD) using PTMS, in accordance with SOP 16. When PTMS is not available, the NIH Problem Report Form will be used.

(https://federation.nih.gov/ohsr/nih/ohrdocs/NIH_Problem_Report_Form_Fillable_DDIR_v1_6-11-13_508.pdf).

All serious UP's and Serious PD's, and will be reported to the IRB and CD as soon as possible but not more than 7 days after the PI first learns of the event. Non-serious UP's will be reported to the IRB and CD, and non-serious PD's to the IRB not more than 14 days after the PI first learns of the event. Deaths will be reported to the Clinical Director within 7 days after the PI first learns of the event. An aggregated summary of all UP's, PD's, and AE's will be reported to the IRB at the time of Continuing Review (CR).

Study Completion

Principal Investigator will maintain subjects' records for at least three years after completion of the study.

EVALUATION OF RESULTS

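### Fractures are exempt from adverse event reporting for a reason unrelated to drug safety, and no fracture count is planned in the untreated or the treated year

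*Protocol*

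**What the plan says.** The Adverse Events section gives the background to the rule: "Fractures may not be consistently documented by x-ray or history, and can occur in clusters". It concludes that "fracture incidence is not an accurate measure of progression or worsening of osteogenesis imperfecta", and then sets the rule: "Fractures are not defined as reportable adverse events".

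Four other places bear on it:

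- The Introduction describes the disease as having "bone fragility as the hallmark feature". It lists among the aims of the earlier 28-child investigation "whether OI bone could be safely stimulated to grow".
- Part A makes the pre-treatment interval a "one year time period during which children will be serving as their own baseline controls". Visits are 3-monthly and spine and leg films 6-monthly, and Part B continues the same parameters in the treatment year.
- Adverse Event Procedures and Documentation says: "An aggregated summary of all UP's, PD's, and AE's will be reported to the IRB at the time of Continuing Review".
- IRB and DSMC Documentation says that the study does not meet the criteria for sending data to a data safety monitoring committee.

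**The concern.** The conclusion is wider than its premise. That an event tracks disease progression poorly is a reason not to use it as an efficacy measure. That it is frequent and expected is a reason not to send an expedited report each time. Neither is a reason to leave it uncounted when the question is whether a drug changes its rate.

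The drug here stimulates growth in bone that is fragile by definition, and children who keep responding stay on it until final adult height. The protocol measures possible bone benefit through density and histomorphometry. It plans no matching count of the most obvious clinical bone harm, although the untreated year provides a within-child reference and no monitoring committee stands behind the investigators.

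**Working it through.** **Is there a fracture count anywhere?** I looked for one section by section.

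| Place in the protocol | Fracture item |
|---|---|
| Objectives (four) | none |
| Part A measurement list and visit table | none; 6-monthly spine and leg films, no fracture reading specified |
| Part B visit table | none; continues the Part A parameters |
| Off Study Criteria | none |
| Adverse Events | declared not reportable |
| Adverse Event Procedures and Documentation | all adverse events aggregated for the IRB; fractures not mentioned |
| Evaluation of Results | none |

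The two adverse event sections do not settle each other. One removes fractures from reportable events. The other promises an aggregate of all adverse events and does not say whether the exemption carries over.

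**How much could a count show?** The protocol has no fracture rate or fracture power figure to reproduce. Its only power figure is 91% for the responder test with 20 children. It reproduces at an assumed one-sided 0.05: (0.5 − 0.2 − 1.645 × √(0.16/20)) / √(0.25/20) = 1.37, power 0.914. I take only the 20 from it. The title page gives 60 as the recruitment total.

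Assumptions: one untreated and one treated year per child, a mean of 1 or 2 fractures per untreated year, and a doubling on treatment.

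*Conditional binomial test.* Expected totals are 20 × 1 × (1 + 2) = 60 or 20 × 2 × (1 + 2) = 120 fractures. Given the total, the treated share is 1/2 under no effect and 2/3 under a doubling.

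*Clustered counts.* Each mean is multiplied by a gamma variable (shape 1), and the test is the Wilcoxon signed-rank. The multiplier is either drawn afresh each year or kept as a stable trait of the child. Simulated values are good to about 0.02.

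| Model | Children | Test at 0.05 | Mean 1 | Mean 2 |
|---|---|---|---|---|
| Poisson | 20 | one-sided | 0.80 | 0.98 |
| Clustered, fresh each year | 20 | one-sided | 0.45 | 0.51 |
| Clustered, fresh each year | 20 | two-sided | 0.32 | 0.37 |
| Clustered, stable child trait | 20 | one-sided | 0.76 | 0.94 |
| Clustered, fresh each year | 60 | one-sided | 0.86 | 0.91 |

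For a 1.5-fold rise with fresh clustering and 20 children, power is about 0.21 to 0.25 one-sided and 0.13 to 0.15 two-sided.

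*Closed-form cross-check.* Use a log rate ratio with overdispersion factor φ, two-sided 0.05 and 20 children. At mean 1, SE = √(φ(1/20 + 1/40)) and power = Φ(0.693/SE − 1.96). For φ = 1, SE = 0.274 and power is 0.72. For φ = 4, SE = 0.548 and power is 0.24. At mean 2 the corresponding powers are 0.95 and 0.43.

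The protocol itself says that fractures cluster, so the Poisson row is a best case.

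**The case against.** The case for the rule is that it is a disclosed and reasoned choice. Fractures are expected in this disease and unevenly documented, and an IRB could accept exempting them. That stands for expedited reporting, and the fix leaves it alone.

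A reader might go further and infer that a rise in fractures would go wholly unseen, or that the trial could never show harm. The protocol does not support that. Films are taken 6-monthly in both years, families may bring home films for copying, and unanticipated problems still go to the IRB. Some fractures could come to light and be reviewed later. Non-reportable is also not the same as unrecorded: case report forms and the co-enrolled protocol 97-CH-0064 are not shown, although only pulmonary and neurological testing is taken from the latter here. Nor does the text state that the IRB summary leaves fractures out; it is unclear on that.

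Three further points stand:

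- Safe stimulation of bone was an aim of the earlier investigation and is not one of the four current objectives.
- Equal under-recording in both years is an assumption. The treated year always comes second, so age, mobility and parental attention may change both the true rate and its reporting.
- The Consent section says that contact is lost with about three quarters of patients, so prospective counts are not available for many.

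These limit what a fracture table can prove. They do not supply a reason for having none.

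**Conclusion.** The point holds in a limited form. The stated reason for the exemption does not address drug safety. The protocol plans no fracture count in either year, and whether the continuing-review aggregate includes fractures is unresolved. Followed as written, it has no planned comparison that would show a rise on treatment.

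The size is modest and rests on assumptions. With 20 children, an assumed 1 to 2 fractures per untreated child-year and strong year-to-year clustering, a doubling would be detected with about 30% to 50% power, depending on the test's sidedness. Power is higher if clustering is a stable trait of the child or if all 60 recruits contribute. A smaller rise would usually be missed, and a null result would not establish safety. The change is worth making for descriptive safety information.

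**What to change.** - Keep fractures exempt from individual expedited reporting.
- At each 3-monthly visit in Parts A and B, record every fracture since the last visit with date, site, and whether it was confirmed on film or only reported.
- Tabulate fractures per child-year, untreated against treated. Show the first treated year separately, because only responders continue after it.
- State that the continuing-review summary includes this table, which settles the unclear scope of the aggregate.
- For children already past these visits, use existing records and films where available, and report how many children contribute.
- Label the table descriptive, and name the clustering and the confounding by age, mobility and reporting.

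The cost is one data field at existing visits and one table, plus some retrospective review of records and films. The downside is noisy counts that could be over-read.

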RESPONDERS 6	Х	Х		Х	Х		
MONTH							
12 MONTH	Х	Х	X	Х	Х		
TREATMENT	Х	Х	X	Х	Х		
END, 3 YEAR							
NON-							
RESPONDERS							
ADULT	X	X	X	Х	X		
STATURE							

Parameters which will be followed during the treatment year will be a continuation of those followed during the pre-treatment year, and are summarized in the following table:

All visits will be outpatient day hospital visits with the exception of those visits when a bone biopsy is scheduled.

MONITORING SUBJECTS, DOSAGE, AND CRITERIA FOR WITHDRAWAL OF SUBJECTS FROM THE STUDY

Treatment with Humatrope[®] will begin at the 12 month pretreatment visit/baseline treatment visit. The accompanying parent will learn how to reconstitute the drug and administer the subcutaneous injections. The dose will be 0.06 mg/kg/day for 6 days of the week. At the end of 12 months of treatment, those children who have responded with a

sustained 50% increase in growth rate will remain on Humatrope[®] injections for an additional 2 years. After the third year of treatment, responders will be defined as those children who demonstrate a sustained increase of 30% or greater above baseline. These responders will be treated through attainment of final adult height as defined above.

STRATIFICATION AND RANDOMIZATION

All patients entering this study will undergo the same protocol as described above. There will be no randomization.

HUMAN SUBJECTS PROTECTIONS

Children enrolled in this study will be limited to those with Sillence Types III and IV OI, as determined by clinical and genetic criteria. This disorder is autosomal dominant, and occurs with equal distribution in males and females. The disorder has been described in all races and has no ethnic preference. There are no exclusionary criteria related to race or gender for this protocol.

CRITERIA FOR PATIENT SELECTION

Patients will be recruited with the goal of including at least 10 each of individuals with clinical/biochemical criteria of types III and IV OI who are between 3 and 8 years of age.

1. Height: Individuals with type III OI have severe short stature by definition; individuals with type IV OI recruited to the study will have height less than the 3rd percentile for age. All individuals will be required to furnish growth records, especially height and head circumference, from at least the preceding two years.

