The primary outcome is the change in growth rate from untreated to treated status. For the first year, a 50% increase in growth rate is considered a positive response. We suppose that growth rate is approximately normally distributed. From random chance, we estimate that the probability of observing a 50% increase in growth without intervention is less than 0.2. Therefore, we would like to test the null hypothesis that the proportion of responders in the population is less than or equal to 0.2 against the alternative that the proportion exceeds 0.2. Using a normal approximation to the binomial and assuming the true action of GH is to result in a population with mean 50% more than the untreated mean, we have 91% power with the sample size of 20.

Other protocol parameters will be correlated with linear growth responders versus nonresponders, as well as being analyzed for the group as a whole. These correlations will be made for both 6 month and one-year treatment intervals throughout the study.

NATURE OF FINANCIAL COMPENSATION

No financial payments will be offered to patients or their families.

References

- Marini JC, C.E., Osteogenesis Imperfecta, in Management of Genetic Syndromes, A.J. Cassidy SB, Editor. 2001, Wiley-Liss: New York. p. 281-300.
- 2. Marini, J.C., Osteogenesis imperfecta: comprehensive management. Adv Pediatr, 1988. 35: p. 391-426.
- 3. Ernst, M. and E.R. Froesch, *Growth hormone dependent stimulation of osteoblast-like cells in serum-free cultures via local synthesis of insulin-like growth factor I.* Biochem Biophys Res Commun, 1988. **151**(1): p. 142-7.
- 4. Rauch, F., et al., *Static and dynamic bone histomorphometry in children with osteogenesis imperfecta.* Bone, 2000. **26**(6): p. 581-9.
- 5. Prockop, D.J. and K.I. Kivirikko, *Heritable diseases of collagen*. N Engl J Med, 1984. **311**(6): p. 376-86.
- Prockop, D.J., et al., *The biosynthesis of collagen and its disorders (first of two parts)*. N Engl J Med, 1979. **301**(1): p. 13-23.
- 7. Cohen, P., et al., Consensus statement on the diagnosis and treatment of children with idiopathic short stature: a summary of the Growth Hormone Research Society, the Lawson Wilkins Pediatric Endocrine Society, and the European Society for Paediatric Endocrinology Workshop. J Clin Endocrinol Metab, 2008. 93(11): p. 4210-7.
- 8. Rose, S.R. and G. Municchi, *Six-hour and four-hour nocturnal sampling for growth hormone*. J Pediatr Endocrinol Metab, 1999. **12**(2): p. 167-73.

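### No responder cut-off with 20 children gives the stated 91% power; the rule that holds a one-sided 5% level (8 or more of 20) has 86.8%

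*Protocol*

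**What the plan says.** All the design figures are in the protocol's Evaluation of Results section. The primary outcome is the change in growth rate from untreated to treated status, and for the first year "a 50% increase in growth rate is considered a positive response". The test is of "the null hypothesis that the proportion of responders in the population is less than or equal to 0.2". It is one-sided, because this null is set "against the alternative that the proportion exceeds 0.2". The power statement rests on three assumptions:

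- Distribution: "We suppose that growth rate is approximately normally distributed".
- Effect: "assuming the true action of GH is to result in a population with mean 50% more than the untreated mean".
- Method: "Using a normal approximation to the binomial".

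From these the protocol concludes "we have 91% power with the sample size of 20". The section gives neither a significance level nor the number of responders at which the null would be rejected.

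The number 20 matches the recruitment goal under Criteria for Patient Selection, which is to recruit children aged 3 to 8 "with the goal of including at least 10 each of individuals with clinical/biochemical criteria of types III and IV OI".

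**The concern.** With 20 children the number of responders is a whole number, so only a few combinations of type I error and power exist. A normal approximation without continuity correction ignores this. It places the critical value between two whole numbers and reports the power at that point. The expected number of responders at the null boundary is only 20 × 0.2 = 4, where this matters.

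Two things are at stake. The first is the power figure itself, which is the protocol's justification for 20 children. The second is the reading of a borderline result. The uncorrected approximation would reject at 7 of 20, while an exact or continuity-corrected test at the same level would not reject until 8 of 20.

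**Working it through.** **Inputs**

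- n = 20, null proportion p0 = 0.2, one-sided upper alternative: stated in Evaluation of Results.
- p1 = 0.5: inferred. If growth rate under treatment is normal with mean 50% above the untreated mean, half the children lie above the 50% response threshold.
- One-sided alpha = 0.05: assumed, because none is stated. Of the three conventional levels tried, it is the only one that reproduces the stated figure in step 1.

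**Step 1. Reproduce the protocol's figure (normal approximation, no continuity correction)**

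- Critical proportion = p0 + z × √(p0(1 − p0)/n) = 0.2 + 1.645 × √(0.16/20) = 0.3471, which is 6.94 of 20 children.
- Power = Φ((p1 − 0.3471)/√(p1(1 − p1)/n)) = Φ((0.5 − 0.3471)/√(0.25/20)) = Φ(1.367) = 0.914.

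This matches 91%. At alpha 0.025 the same formula gives 86.8%, and at 0.10 it gives 95.1%.

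**Step 2. Add the continuity correction**

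- Critical count = 6.94 + 0.5 = 7.44, so rejection starts at 8 of 20.
- Power = Φ((0.5 − 0.3471 − 0.025)/√(0.25/20)) = Φ(1.144) = 0.874.

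**Step 3. Exact binomial, X ~ Bin(20, p)**

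| Reject if responders are at least | Type I error, P(reject) at p = 0.2 | Power, P(reject) at p = 0.5 |
|---|---|---|
| 7 | 8.7% | 94.2% |
| 8 | 3.2% | 86.8% |
| 9 | 1.0% | 74.8% |

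Power jumps from 86.8% to 94.2% between adjacent cut-offs, so no rule gives 91% whatever alpha is chosen. The smallest cut-off that holds 5% is 8 of 20.

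**Step 4. The borderline result, 7 of 20 (35%)**

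- Uncorrected: z = (0.35 − 0.2)/√(0.16/20) = 1.677, one-sided p = 0.047.
- Continuity-corrected: z = (0.325 − 0.2)/√(0.16/20) = 1.398, p = 0.081.
- Exact: P(X ≥ 7 | p = 0.2) = 0.087.

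The first is significant at 0.05; the other two are not.

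**Step 5. How far the 8.7% reaches**

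The type I error of the 7-of-20 rule depends on the true chance rate: 8.7% at 0.20, 5.0% at about 0.177, 4.1% at 0.17 and 2.2% at 0.15.

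**Step 6. Exact one-sided 5% test at nearby sample sizes (p1 = 0.5)**

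| Children analysed | Cut-off | Type I error | Power |
|---|---|---|---|
| 18 | 8 | 1.6% | 76.0% |
| 19 | 8 | 2.3% | 82.0% |
| 20 | 8 | 3.2% | 86.8% |
| 21 | 8 | 4.3% | 90.5% |
| 22 | 9 | 2.0% | 85.7% |
| 23 | 9 | 2.7% | 89.5% |
| 24 | 9 | 3.6% | 92.4% |

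Power does not rise steadily with n, because the cut-off moves in whole steps.

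**The case against.** The strongest reply is that nothing is miscalculated. The protocol names its method, the method yields 91%, and preferring an exact calculation is a choice. If the uncorrected approximation were also the final test, exact power would be 94.2%, so 91% would understate it. That is true as far as it goes, but that rule carries an 8.7% error at the null boundary, and the stated null includes 0.2. The 91% still describes neither available rule.

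A second reply is that the level, the final test and the cut-off may properly be left to a statistical analysis plan. This is fair, and their absence alone would not be a finding. The 8.7% applies only if the uncorrected test is used, and the protocol does not prescribe it for the analysis. But no later choice of test for 20 children can make the 91% correct.

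Third, the effect is modest and sensitive to p1. The protocol's Introduction reports 19 responders among 36 treated children (52.8%), and at that rate the 8-of-20 rule has exact power of 91.5%. The title page lists 60 patients to be recruited, and at least 10 of each type is a floor. With 21 children, exact power is 90.5%, which is about 91% in whole percent. These points limit the practical weight, and power at 20 stays above 80%. They do not rescue the statement, which is made for 20 children and for the effect assumption that implies 0.5.

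**Conclusion.** The concern holds. The 91% comes from treating a critical count of 6.94 children as attainable. With 20 children and a true response rate of 0.5, a one-sided 5% test has 86.8% power exactly, or 87.4% by the continuity-corrected approximation. That is about 4 points below the stated figure.

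That no cut-off yields 91% depends only on p1 = 0.5, which follows from the protocol's normality and mean-shift assumptions. The 86.8% also depends on the assumed one-sided alpha of 0.05. The 8.7% type I error is conditional: it needs the uncorrected approximation as the final test and a true chance rate at the boundary of 0.2.

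There is little slack if only 20 children are enrolled: one fewer analysed lowers exact power to 82.0%, two fewer to 76.0%. The statement should be corrected, but the design remains workable.

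**What to change.** Replace the power sentence in Evaluation of Results with wording such as:

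> The responder proportion will be tested with a one-sided exact binomial test at alpha 0.05 of p ≤ 0.2 against p > 0.2. With 20 children analysed, the null is rejected if 8 or more respond (actual size 3.2%); power is about 87% if the true response rate is 0.5. If the number analysed differs from 20, the cut-off is recomputed for that number.

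The cost is one paragraph of text and no additional patients. The quoted power falls by about 4 points, and a result of exactly 7 of 20 no longer counts as positive. If the sponsor prefers to keep at least 91%, the first sample size at which the exact test reaches it is 24 analysed children (9 or more responders, power 92.4%); 21 children (8 or more) come close, at 90.5%.
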